8.0 Data Collection and Management Procedures

The overall goals of data management are to ensure: 1) that the collected data is properly documented and accurately entered; 2) the confidentiality of the participant data is maintained giving access to the primary investigators for retrieving data and exporting to statistical packages. A codebook will be created consisting of Prior to data collection and entry, a codebook will be created which will contain the variable names, descriptions, and value codes of each variable/item collected during the study. Following development of the codebook, a database will be created in Microsoft Excel to facilitate data entry. The program permits logic checks on input and checks for invalid entries. One research staff member will enter all data separately, and another researcher will verify the data entry to identify any mismatching data values, variable names, or observation numbers thus, to eliminate data entry errors. Several data quality checks will also be conducted, including descriptive statistics and graphic plots to detect outliers and influential observations. All computer data will be stored in a passwordprotected network server with back-up scheduled every midnight. The original raw data will be stored in a locked cabinet accessed only by key project personnel. The motion analysis data would be backed up on a portable hard drive and stored in a locked cabinet accessed only by key project personnel.

Each laboratory session will be recorded with a video camera system for further analysis of body responses. The 3D motion cameras will detect small ball-shaped markers that is placed on different parts of the body, including the feet, ankles, knees, hips, shoulders, elbows, and wrists to represent body movement. Each session will also be recorded on a videotape using a camcorder. Only the investigators related to this project will have access to these files. The videotape or its reproduction may be used for research purposes such as publication in scientific journals or presentations at educational or scientific meetings and teaching purposes in the future. All the videos are taken from the side and back, where no facial feature will be identifiable. Thus, the participant would not be recognizable by a stranger without other identification from the record. ID codes will be at a single office and in a locked file. They will be destroyed along with the videotape of the experiment 2 years after completion of the entire project. Only the personnel directly related to the project will have access to the videotape, which is kept in a locked office. Only the Principal Investigator and one research team member have the access key, and there are no duplicate keys.

For Group 1 and 2: All the details described above will be used for data collection and storage.

For Group 3 (online assessments and online training: Data including assessment measures (online assessment procedures are described in assessment section) will be

collected via HIPAA complaint 'Zoom' version (described in 'Safety' section). The participants performance will be scored on observational basis which will be noted on hard copy of the trial record sheet for testing. During the training sessions, the participants will read out their heart rate and number of steps which is displayed on their wrist monitor to the research personnel after every sub-session and the research personnel will note this down on the hard copy training sheet. The participant will be informed prior to recording the testing and training sessions to ensure that he/she is aware of it. Their consent for video recording is mentioned and clarified in the informed consent that videos will be recorded if they participate in the study. However, they can opt out of their videos being used for education purposes or conferences. The video files will be in the form of mp4 and this will be used for analysis purposes. No personal health information or contact information will be recorded to ensure participants privacy. Each participant will be denoted with a subject number and testing and training video files will be directly stored under subjects specific denoted number.

9.0 Data Analysis

All the data analysis will be performed at [name] using the SPSS Inc., (Armonk, NY). Also, see the section "Statistical Considerations".

10.0 Quality Control and Quality Assurance

For quality control and assurance, all the study related procedures will be performed by trained and experienced personnel. All research personnel will take the CITI and HIPAA training courses along with regular training to ensure safety of the custom designed equipment. The raw data will be checked by the PI immediately after data collection.

11.0 Data and Safety Monitoring

There will be a dual data and safety monitoring plan in place. One which is monitored by the research team itself and the second which is monitored by a Data and Safety Monitoring Board/Committee (DSMB).

The Principal Investigator (PI) [name] will be responsible for ensuring participants' safety daily. In addition, other individuals the Safety Officer in conjunction with a Data Safety Monitoring Roybal Center Committee will act in an advisory capacity to monitor participant safety, evaluate the progress of the study, to review procedures

for monitoring the confidentiality of the data, the quality of data collection matter, management, and analyses.

For monitoring participant safety during the testing and training sessions, Participants will be asked whether they are feeling any pain or any kind of distress at regular intervals. Participants' heart rate (HR), blood pressure (BP) and blood oxygen levels will be monitored before and after testing, and before, after and during training session. The experiment will be stopped if any discomfort noticed and the HR > 20 bpm of the resting HR or blood oxygen drops below 92% or systolic BP exceeds > 20 mmHg of the resting state or if the diastolic BP exceeds > 15 mmHg from the resting state. There will always be two people in the experiment area to guard the participant if required. There is always a first aid kit available in the lab for use in case of any minor injury. We also have an AED for emergencies and at least one of the investigators during any experiment will be AHA-BLS (American Heart Association - Basic Life Support) certified for health care providers. In addition, we do regular harness checks to ensure that it is not damaged. Also, the participants will be called 2 days after the testing session and will be asked to inform the research personnel if there is any discomfort during the intervention period.

Adverse Event and Serious Adverse Event Collection and Reporting

An adverse event is defined as an undesirable and unintended result of therapy, intervention or interaction experienced by a participant in a research study. We will monitor adverse events, reports by participants during the intervention and maintenance phases of the study and reasons for drop out. All field staff who work directly with participants will be required to notify the PIs of any unanticipated problems/adverse events immediately upon discovery. If an adverse event is recorded during the intervention session, the session will be concluded, and the event reported to their physician and to the investigators.

Participants who report the event and will notify the University IRB. The PIs will immediately notify the Data Safety Monitoring Board and the University Institutional Review Board.

The relationship of the adverse event as not related, possibly related or definitely related will be determined using standard criteria for clinical trials and any additional guidelines used/ developed by the Data Safety Monitoring Board and the University Institutional Review Board.

Possible - to qualify, the adverse event must meet 2 of the following conditions:

- 1) Has a reasonable temporal relationship to the intervention,
- 2) Could not readily have been produced by the Participant's clinical state,

- 3) Could not readily have been due to environmental or other interventions,
- 4) Follows a known pattern of response to intervention,
- 5) Disappears or decreases with reduction in cessation of intervention.

Probable - to qualify, the adverse event must meet 3 of the following conditions:

- 1) Has a reasonable temporal relationship to the intervention,
- 2) Could not readily have been produced by the Participant's clinical state,
- 3) Could not readily have been due to environmental or other interventions,
- 4) Follows a known pattern of response to intervention
- 5) Disappears or decreases with reduction in cessation of intervention.

Definite - to qualify, the adverse event must meet at least 4 of the following conditions:

- 1) Has a reasonable temporal relationship to the intervention,
- 2) Could not readily have been produced by the Participant's clinical state,
- 3) Could not readily have been due to environmental or other interventions,
- 4) Follows a known pattern of response to intervention,
- 5) Disappears or decreases with reduction in cessation of intervention

Protection against Study Risks.

Informed Consent Process.

A copy of the consent form approved by UIC IRB will be provided to the potential participants to follow verbal description and to read on their own. Research assistant or research personnel will describe the study procedures verbally including testing, training, potential risks and benefits. Potential participants will be given time to read the consent form and may ask any questions regarding the study to clarify the misunderstandings. Individuals interested in participating at this point will be asked to sign two copies of the written consent form and will be provided with one copy for their use.

Protections against Study Risk. We believe that there is a minimal risk of injury to the participants in this study. These risks include a slight risk of muscle soreness associated with increased physical activity or stretching during training sessions, and a leg or shoulder muscle pull, and leg or back sprain due to expose to unexpected slipperturbation during the testing session. There may also be the risk of anxiety due to the slip test. In case of any injury, participants will be encouraged to (a) consult their primary health care provider before initiating any new physical activity; and (b) perform physical activities at a pace that is comfortable for them and in a way that is consistent with any recommendations from their medical providers. Other risks include the following:

- While performing the blood pressure test, the cuff squeezed may elicit some discomforts.
- The clinical balance tests present a mild risk of losing balance while performing the activities.
- During the cognitive assessment, which tests memory, attention, comprehension, etc., may cause some disappointment and/or anxiety if they are unable to perform a certain task.
- The falls and physical activity questionnaire may have some questions about personal health information and daily physical activity habits, may be uncomfortable answering those questions. In that case, they have the option not to answer those questions.
- Further, as all tests will be performed in a laboratory setting wherein the research personnel will be performing the assessments and training, there is a potential for breach of privacy and confidentiality at any time.
- There may be risk of loss of confidentiality due to participation in this study.

To ensure confidentiality of all data, all participants will be assigned a numerical code and their data will be stored with the same corresponding code. Any identifying information that corresponds to the code number will be stored in a separate and double password-protected file. Access to this file will be limited to the PI and study research assistant/coordinator. Personal or private identifiable data will not be stored on portable devices. Data in paper format, such as consent documents, will be stored in locked file cabinets in a locked office and will only be accessible by immediate project personnel.

All coded electronic data will be stored and secured via password access on the Institute for Health Research and Policy (IHRP) protected server. The IHRP server systems are in a climate controlled locked room that is accessed by ID card. The hardware is protected by several APC UPS systems. The IHRP network uses Windows 2008 R2 Active Directory to control access to files and folders. The system is firewalled off from the rest of the university. The network is a private IP based system that permits us to restrict sensitive machines from connecting to the internet. There is no wireless access directly into the IHRP system. Encrypted backup tapes are stored off-site with Iron Mountain. Data analysis will be conducted with the use of coded data, thereby greatly reducing the chance of inadvertent disclosure.

All project staff will be required to be current in training in Human Research Participants protection sponsored by the University of Illinois at Chicago. The staff will also receive additional training on confidentiality by the principal investigator.

We do not anticipate any serious adverse events or distress as a result of participating in the proposed research. Any concerns will be immediately reported by the principal investigator. The Principal Investigator is a clinical psychologist and will provide training on identifying and responding to emotional distress in participants. For medical emergencies, staff will be trained to immediately call 9-1-1.

Frequency of Data and Safety Monitoring/ Safety Officer (SO) Reports.

The PI will meet semiannually with the DSM Committee, either in-person or by teleconference call to review study progress, data quality, and participants' safety. Written summary reports will be submitted twice a year and will include a detailed analysis of study progress, data and safety issues. [name] will serve as chair of the committee, and as SO for any adverse event reports. Other members will include [name] (Kinesiology), [name] (Medicine), and [name] (School of Public Health).

The PI will be informed of serious adverse events as soon as they occur and will notify the SO within 24 hours of notification. In addition, serious adverse events will be reported to the UIC IRB with their established protocols.

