6.0 Study Design and Procedures

- This study will be a randomized controlled design.
- During the telephone screening, all the participants will be asked to choose a group that
 they prefer to participate which includes 3 options: Group 1: In-person assessments
 and in-person training; Group 2-In-person assessments and online training and Group
 3- Online assessments and online training.

[figure not shown]

- Figure 1 above shows recruitment and distribution of participants into differenct groups based on the options given for assessment and training to the participants during telephone screening.
- After the participants are allocated to groups 1,2 and 3 depending on their choice, each
 participant from every group will be randomly assigned either Group A (CogXergaming)
 or Group B (Matter of balance) for training by flipping a coin.
- Al the participants will be undergo 1-on-1 testing and training.
- Study protocol will vary according to the groups that the participants choose to be in (Groups 1,2 or 3).
- For Group 1 (In-person assessments and in-person training): Group A (CoXergaming) will undergo a total of 8 weeks session with first week and last week comprising of assessment. 6-week training will be delivered using the Nintendo Wii-Fit gaming system and a pointer mouse. Participants will visit the laboratory 3 times a week for 6 weeks with each session lasting for 60 minutes (18 training sessions). During training session, participants will wear a gait belt and will be guarded by a research assistant for safety. On the other hand, if the Group 1 participant gets assigned to Group B (Matter of balance) then participants from Group B will undergo a total of 10 weeks session with first week and last week comprising of assessment. The participants will undergo an 8-week (one session a week for 2 hours/day, 8 sessions in total) structured intervention specifically designed to reduce the fear of falling and to increase the engagement in PA.

| Test | Pre- test | CogXergaming/TeleXercise Intervention (6 weeks) | | | | | | | | | | | Post-test | | | | | | | |
|---------|--------------|---|---|---|---|---|---|---|---|---|----|----|-----------|----|----|----|----|----|----|-----|
| Session | 1-4 | 1 | 2 | 3 | 4 | 5 | 6 | 7 | 8 | 9 | 10 | 11 | 12 | 13 | 14 | 15 | 16 | 17 | 18 | 1-3 |
| Week | 1 | 2 | | 3 | | 4 | | 5 | | 6 | | | 7 | | | 8 | | | | |

| Test | Pre-test | M | latte | Post-test | | | | | | |

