|---------|----------|---|-------|-----------|---|---|---|---|---|-----|
| Session | 1-4 | 1 | 2 | 3 | 4 | 5 | 6 | 7 | 8 | 1-3 |
| Week | 1 | 2 | 3 | 4 | 5 | 6 | 7 | 8 | 9 | 10 |

Protocol design

- For Group 2 (In-person assessments and online training): The assessments will be performed same as Group 1 (in-person). For training sessions, Group A (CoXergaming) will be trained through TeleXercise intervention via zoom online application (details are provided in the intervention section) for 6-weeks. All participants will be undergoing 3 training sessions per week for 6 weeks (18 training sessions). Group B (Matter of balance) will also be trained online and will undergo an 8-week (one session a week for 2 hours/day) structured intervention specifically designed to reduce the fear of falling and to increase the engagement in PA.
- For Group 3 (Online assessments and online training): The assessments will be performed online during the first and the last week. The online pre and post

assessments would consist of assessing balance, gait, cognitive performance and physical activity online via zoom application (details provided in outcomes). For the training sessions, Group A (CoXergaming) will be trained through TeleXercise intervention via zoom online application (details are provided in the intervention section) for 6-weeks. All participants will be undergoing 18-training sessions over a period of 6 weeks. Group B (Matter of balance) will also be trained online and will undergo an 8-week (one session a week for 2 hours/day) structured intervention specifically designed to reduce the fear of falling and to increase the engagement in PA.

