Participants will undergo matter of balance training for 8 weeks (one session a week for 2 hours/day). The program emphasizes practical coping strategies that include group discussions, mutual problem solving, exercises to improve strength, coordination and balance, and a home safety evaluation. The program will be offered by graduate and post-doc research associates in the UIC Physical Therapy Department who will be certified A Matter of Balance (AMOB) coaches. The details of the exercise intervention are provided in the manual attached. Similar intervention for AMOB training will be provided online for participants in Group 2 and Group 3. All the online training sessions will be carried out on 1-on-1 basis.

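### Symptom questioning follows the training schedule (3 sessions a week in arm A, 1 in arm B), so recorded between-session adverse events per participant-week are likely to be biased upward in arm A

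*Combined protocol and SAP*

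**What the plan says.** Section 11.0 (Data and Safety Monitoring) sets the symptom question inside sessions: "For monitoring participant safety during the testing and training sessions, Participants will be asked whether they are feeling any pain" or distress. Outside sessions it gives a telephone call two days after testing, and participants are "asked to inform the research personnel if there is any discomfort during the intervention period". The adverse event paragraph of the same section adds monitoring of participants' own reports and of reasons for dropping out, without an interval or a recall window.

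Section 6.0 fixes how often the arms are seen. For in-person arm A: "Participants will visit the laboratory 3 times a week for 6 weeks with each session lasting for 60 minutes (18 training sessions". For in-person arm B: "8-week (one session a week for 2 hours/day, 8 sessions in total". The online versions keep the same pattern; for arm A in Group 2, "All participants will be undergoing 3 training sessions per week for 6 weeks (18 training sessions". Each arm has one assessment week before training and one after it.

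Other places that might hold a common enquiry do not state one:
- The two-weekly laboratory visit in section 6.4 (Aim 2) is for uploading activity data.
- The helper's observations in section 7.0 are made during sessions.
- Section 11.0 notes that "The falls and physical activity questionnaire may have some questions about personal health information", but neither Table 1 nor the test descriptions in section 6.4 list a falls questionnaire.

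Section 12.0 plans ANCOVA of balance, cognitive, gait and cardiovascular measures and no analysis of adverse events by arm.

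**The concern.** A fall at home, a dizzy spell or soreness between sessions reaches the record if it is still felt when staff next ask, or if the participant mentions it. In arm A the next session is two or three days away; in arm B it can be seven. More events will have resolved or been forgotten over the longer gap, so a difference in recorded rates could reflect contact frequency and not the training.

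This matters because the participants are frail, lower fall risk is a stated expected benefit (section 7.0), the monitoring committee receives safety reports twice a year, and the study is meant to inform a larger trial. More events during sessions in arm A would be a genuine result of more exposure. Unequal capture between sessions is not.

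**Working it through.** **Inputs from the documents.** Arm A: 3 × 6 = 18 sessions. Arm B: 1 × 8 = 8 sessions. Both match section 6.0. Scheduled asking is 3 a week against 1 a week (ratio 3); in total, 18/8 = 2.25. Training weeks: 6 against 8.

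**Assumed, because the documents give no figure.** Equal true weekly rates in both arms; how far back a participant will mention an event (d); mean event duration (D); the probability of volunteering an event (v), equal in both arms. All are shown as ranges.

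**Check 1: spontaneous mention within d days of a contact.** Gaps in A are 2, 2 and 3 days; in B, 7 days. Share captured: A = [min(d,2) + min(d,2) + min(d,3)]/7; B = min(d,7)/7. Count ratio = (6/8) × rate ratio.

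| d (days) | A | B | Weekly rate ratio A/B | Raw count ratio A/B |
|---|---|---|---|---|
| 2 | 6/7 = 86% | 2/7 = 29% | 3.0 | 2.25 |
| 3 | 100% | 3/7 = 43% | 2.3 | 1.75 |
| 5 | 100% | 5/7 = 71% | 1.4 | 1.05 |
| 7 | 100% | 100% | 1.0 | 0.75 |

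For d of 2 days or less the rate ratio stays at its ceiling of 3, the ratio of weekly contacts. Raw counts are equal where 6 = 8d/7, that is d = 5.25 days.

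**Check 2: symptom still present when asked.** This is closer to the wording about current feeling. An event starts at a uniform time and lasts an exponential time with mean D. It is recorded if still present at the next session (gap T = 7/3 days in A, 7 days in B) or if volunteered: p(T) = v + (1 − v)(D/T)(1 − exp(−T/D)).

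Example with v = 0, D = 1: A = (3/7)(1 − exp(−7/3)) = 0.387; B = (1/7)(1 − exp(−7)) = 0.143; rate ratio 2.71; count ratio 0.75 × 2.71 = 2.03.

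| v | D (days) | p, arm A | p, arm B | Rate ratio | Count ratio |
|---|---|---|---|---|---|
| 0 | 1 | 0.387 | 0.143 | 2.71 | 2.03 |
| 0 | 3 | 0.695 | 0.387 | 1.80 | 1.35 |
| 0 | 7 | 0.850 | 0.632 | 1.35 | 1.01 |
| 0 | 14 | 0.921 | 0.787 | 1.17 | 0.88 |
| 0.25 | 1 | 0.540 | 0.357 | 1.51 | 1.13 |
| 0.25 | 7 | 0.888 | 0.724 | 1.23 | 0.92 |
| 0.50 | 1 | 0.694 | 0.571 | 1.21 | 0.91 |
| 0.50 | 28 | 0.980 | 0.942 | 1.04 | 0.78 |
| 0.75 | 28 | 0.990 | 0.971 | 1.02 | 0.76 |

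The rate ratio is above 1 in every case tried. The raw count is higher in A only for D below about 7.2 days at v = 0 or about 4.4 days at v = 0.25, and at none of the durations tried (1 to 28 days) at v = 0.50. Using gaps of 2, 2 and 3 days in place of 7/3 changes the 2.71 to 2.68.

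**Illustration in events.** Take the 48 per arm analysed under section 12.0 (3 × 16) and an assumed true rate of 0.1 per participant-week. True events are 48 × 6 × 0.1 = 28.8 in A and 48 × 8 × 0.1 = 38.4 in B. With v = 0, about 11.1 against 5.5 are recorded at D = 1, and 26.5 against 30.2 at D = 14.

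**After a common weekly question.** Scheduled capture is the same in both arms, so the rate ratio is 1.00. The raw count ratio is still 6/8 = 0.75, which is why a per-week denominator is needed.

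**The case against.** A reader might infer that adverse events are asked about only at sessions and that arm A will therefore show more of them. The documents support neither step. The call after testing and the request to report discomfort apply to both arms, as does the two-weekly upload visit. Arm B's longer training period can leave B with the higher raw count.

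The session question also concerns present feeling, so a fall that left no symptom is directly asked about in neither arm. Arm B's two-hour sessions deal with fear of falling and home safety, where a recent fall may well come up unprompted; that corresponds to a larger d or v and a smaller bias. The adverse event protocol figure in section 7.0 is not reproduced in the text available, so a common enquiry shown only there cannot be excluded. Finally, section 12.0 plans no comparison of the arms on safety, and section 11.0 handles events one by one through notification and a relatedness grading.

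All of this stands as a limit on size and consequence. It does not remove the imbalance: none of the channels described in the text is a scheduled question with a fixed recall window common to both arms. The call follows testing and does not cover the training weeks evenly.

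**Conclusion.** The concern holds for the rate per participant-week. At equal true rates, recorded between-session events are likely to be biased upward in arm A, by a factor between about 1.0 and 3. The upper end needs short-lived or quickly forgotten events that are seldom volunteered. The bias nearly vanishes when events last weeks or are mostly volunteered, and is nil if participants mention anything from the past seven days. These figures rest on assumed durations, recall and volunteering.

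It would go too far to say that arm A's event count will be higher, or that the safety record must run against CogXergaming: the direction for raw counts is undetermined. The primary analyses are untouched. What is at stake is the semiannual safety reports and any later reading of safety by arm. The change is a cheap improvement worth making, since between-session events not asked about at the time cannot be reliably recovered later.

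**What to change.** In section 11.0, in the session monitoring and adverse event collection paragraphs:

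- Add one identical scripted question in both arms covering the past 7 days: falls, injury, new symptoms and medical contact.
- Ask it once a week at a contact that already exists: the first session of the week in arm A and the weekly session in arm B. Ask it again at post-test, so that the last training week is covered.
- Do not rely on the falls questionnaire mentioned in sections 7.0 and 11.0 unless its content suits 7-day recall.
- Report the events found by this question per participant-week. Report events during sessions separately, per session. Keep events volunteered at other contacts in a third category, because arm A still has two extra contacts a week at which to mention them.

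The cost is a few minutes per participant per week and some extra tabulation. More minor events will be recorded, probably mainly in arm B, and the safety reports should say so.
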